7.1 Medical Record Review

Most data collected for the LITE study should be present in the medical record (source document) as part of routine documentation. Some data may be abstracted from the medical record or documented as part of completing the electronic case report forms (CRF) for the study. Below are examples of some variables which may already be present in the medical record.

- Demographics (year, date of birth, sex, marital status, education, employment status, annual household income, insurance type, race, ethnicity)
- Height
- Weight
- PGA, BSA
- Prior and concomitant psoriasis treatment
- Psoriasis date of onset
- Psoriatic arthritis presence and date of onset if present
- Major medical comorbidity
- Family history of psoriasis
- Fitzpatrick skin type (description of skin and eye color and skin's reaction to sunlight)
- Psoriasis response to sunlight
- Smoking history
- Alcohol history

7.2 Physical Examination

A complete examination of the skin will be conducted at visit 1 and 2 as well as at any unscheduled visits if deemed necessary by the patient's clinician. A physician global assessment and body surface area affected by psoriasis will be reported from the physical examination.

7.3 Vital Signs

Vital signs may or may not be taken as part of routine evaluation but will not be collected by the study.

7.4 Other Evaluations, Measures

All evaluations are described above and included on the schedule of events, see Appendix D.

7.5 Effectiveness Evaluations

Measurements of effectiveness include PGA, BSA, and the DLQI.

7.6 Safety Evaluations

Safety will be monitored by the local clinicians.

Patients will be queried about the reaction to phototherapy (i.e., burns) immediately prior to each phototherapy treatment as is standard practice. Patients will contact the study clinicians for any significant reaction to phototherapy (a burn which requires medical attention such as one associated with significant pain that interrupts usual activities or skin blistering). Patients will be queried about SAE's at visit 2. Patients can spontaneously report SAEs at any point during the study.

8 Statistical Plan

8.1 **Primary Endpoint**

Primary analyses will be based on the intent to treat (ITT) population defined as all patients meeting eligibility requirements who are randomized to one of the two study arms. In the ITT population, we will compare the two treatment arms with respect to two primary effectiveness outcomes. The first primary effectiveness outcome is treatment response, a dichotomous indicator of whether a patient has achieved clear/almost clear skin (score of 0 or 1), based on the Physician's Global Assessment (PGA) at the earlier of week 12 (visit 2), defined as the twelfth week after the start of treatment, or the time of discontinuation of phototherapy. In our primary analyses, patients who drop out of the study prior to achieving clear/almost clear skin or week 12, whichever comes first, will be classified as treatment failures (i.e., failure to achieve clear/almost clear skin). The second primary outcome is the patient-reported Dermatology Life Quality Index (DLQI) assessed at week 12. We will dichotomize DLQI at a score of 0-5 (corresponding to no to small impact on quality of life) versus a score >5. Patients failing to complete the week 12 DLQI assessment will be assumed to have DLQI >5 and therefore classified as a non-responder on this measure.

We hypothesize that effectiveness of home-based UVB phototherapy will not be inferior to that of officebased phototherapy on either of the two primary effectiveness outcomes. At the conclusion of the trial we will report the response rate, i.e. the proportion of patients achieving clear/almost clear skin on the PGA at the earlier of 12 weeks after initiating home or office-based phototherapy or discontinuation of phototherapy and the proportion of patients with no to small impairment on quality of life (DLQI 0-5) at week 12 for each treatment arm with 95% confidence intervals. These measures will be reported for the complete study cohort and separately for two of the three skin type sub-groups. We will not be able to test the hypothesis of non-inferiority of home vs. office treatment in skin type V/VI. We will accumulate additional data in this group which will improve the precision of our estimates of efficacy in this patient population as well as gather additional data about barriers patients with skin type 5/6 face in accessing home or office base phototherapy that lead to inequities and health disparities in patients with psoriasis.

To account for stratification by skin type, which induces non-independence across strata, pooled analyses will be conducted using logistic regression adjusted for treatment arm and skin type. Skin-type adjusted risk differences between home and office-based phototherapy will be computed from odds ratios using marginal standardization. Statistical inference will be based on adjusted risk differences according to non-inferiority principles. Home-based phototherapy will be determined to be non-inferior relative to office based phototherapy if the lower bound of the adjusted two-sided 95% confidence interval for the risk difference is greater than the pre-specified non-inferiority margin of 15%.

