3.1 General Design

The design is a large pragmatic randomized active comparator study of home vs. office based NB-UVB phototherapy for the treatment of psoriasis. Both comparator treatments are considered standard of care and thus this would be classified as a Phase IV study. Dosing of phototherapy will be based on a standardized protocol (see APPENDIX A) or a standard protocol that is routinely used by the local investigators in order to reflect routine clinical practice. The study will include up to 1050 patients stratified by Fitzpatrick skin type (350 skin type I/II, 350 skin type III/IV, we anticipate that approximately 80 participants will be enrolled in Skin type V/VI). We hypothesize that home phototherapy will be noninferior to office based phototherapy. There will be a recommended screening period of up to 28 days, to allow for obtaining informed consent and administrative procedures necessary for office based or home phototherapy, as well as randomization. Patients will be randomized (1:1) to home vs. office-based phototherapy within 28 days of the baseline visit or per standard of care of individual practices. If the patient is randomized to home phototherapy a machine will be delivered to their home and phototherapy treatment initiated within 14 days of randomization. If the patient is randomized to office phototherapy, the first treatment should occur within 14 days of randomization. The patient will be assessed by the dermatologist (or PA or NP or other gualified clinician as appropriate to the clinical practice) at baseline and at 12 (plus or minus 2) weeks after start of phototherapy, or at the time of discontinuation of phototherapy, whichever comes first. Patients will receive phototherapy treatments about 3 times per week for 12 weeks. They will then be observed for an additional 12 weeks. With each phototherapy treatment, patient response to prior phototherapy treatment will be collected by clinic staff or recorded on the phototherapy machine via patient assessment. Patients will complete a survey every 4 weeks for the duration of the study that captures patient reported outcomes.

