3.1.4 Allocation to Interventional Group

Randomization will be implemented using randomly permuted blocks of size two or four, stratified on clinic and skin type. This will maximize blinding of investigators to the randomization schema and achieve balanced groups within study sites and skin types. A randomization table will be created by the senior biostatistician at the University of Pennsylvania and built into the study application ("app") by the Clinical Research Computing Unit (CRCU). The app will be loaded on iPads used to collect data by the study sites. When a new patient is enrolled in the study, the app will generate a new patient id and provide a treatment assignment. The master list of patient ids and treatment assignments will be stored electronically at the CRCU. Data analysts will be blinded as to group assignment by using codes for randomization groups.

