4.3 Subject Recruitment

Patients will be recruited from approximately 20-40 sites across the United States by dermatologists who offer office-based phototherapy. The patients will be recruited during routine clinical evaluation when the patient and physician (or appropriate provider such as physician assistant or nurse practitioner) are embarking on a course of treatment for plaque or guttate psoriasis.

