5.2 Intervention Regimen

Starting dose will be based on Fitzpatrick skin type (as ascertained by the clinical practice) and will increase based on the patient's response to the treatment. The clinicians will be allowed flexibility in deviating from this regimen based on their local practice. See Appendix A for example standardized protocol.

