8.2 Secondary Endpoints

In addition to pooled analyses described above, separate analyses will be conducted for each skin type using a non-inferiority margin of 15%. The estimated risk difference in dichotomized DLQI at week 12 and PGA at or before week 12 will be estimated empirically based on the proportion of patients achieving the endpoint in each skin type sub-group and study arm. We will also assess heterogeneity of treatment effect (HTE) across the three skin types using logistic regression. In this analysis, we will fit models for each of the two primary outcomes with skin type, treatment arm, and their interaction as predictors. HTE will be assessed using an omnibus Wald test of all interaction regression parameters for each outcome of interest in order to minimize multiple testing and consequent alpha inflation.

In secondary analyses, we will investigate additional outcomes:

- Total number of phototherapy treatments received
- Cumulative dose of phototherapy
- Frequency of topical concomitant psoriasis treatment
- Changes in initiation, dosing, or discontinuation of oral or biologic psoriasis treatments
- Patient-reported amount of time spent on phototherapy
- Patient reported travel (cost and time)
- DLQI score of ≤1at week 12

- MCID on DLQI at week 1245
- Physician reported change in the product of body surface area (BSA) times PGA (both as a continuous measure and as a dichotomous measure evaluating a 75% and 90% reduction in the BSAxPGA).
- Duration of treatment response
- Percentage of patients receiving ≥ 80% of assigned treatments

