8.4.4 Exploratory Analysis

In addition to the primary ITT analyses described above, we will conduct an "as treated" analysis in order to evaluate those who completed the study and received at least 80% of treatments. We will evaluate the effects of indirect costs (i.e., co-pays), treatment center, season, geography, and psoriasis characteristics (such as plaque thickness) on response rate. Additional exploratory analysis will be conducted by request of our stakeholder committees upon review of the data (these will be designated post hoc). Exploratory and post hoc analyses will be interpreted with caution and taking into consideration the total number of post hoc comparisons that have been conducted.

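### Clinic is a randomization stratum but is left out of the pooled and skin-type analyses; if clinics differ in response level, the intervals are slightly too wide

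*Combined protocol and SAP*

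**What the plan says.** - **Design.** Section 3.1.4: "Randomization will be implemented using randomly permuted blocks of size two or four, stratified on clinic and skin type". Allocation is 1:1 (section 3.1). Section 4.3: "Patients will be recruited from approximately 20-40 sites across the United States".
- **Pooled analysis.** In section 8.1, "pooled analyses will be conducted using logistic regression adjusted for treatment arm and skin type". The risk difference is then obtained by marginal standardization. The reason given for the skin-type term is that randomization was stratified on it. Clinic, the other stratification factor, is not mentioned.
- **Skin-type analyses.** In section 8.2 the risk difference "will be estimated empirically based on the proportion of patients achieving the endpoint in each skin type sub-group and study arm". There is no clinic term.
- **Other use of clinic.** Section 8.4.4 (exploratory): "We will evaluate the effects of indirect costs (i.e., co-pays), treatment center, season", among other factors. This concerns predictors of response and does not enter any interval used for a non-inferiority decision.
- **Why clinics may differ.** Section 3.1 allows each site's routine dosing protocol, and section 5.2 adds: "The clinicians will be allowed flexibility in deviating from this regimen based on their local practice". Section 7 has the PGA scored by the local physician or a designee.

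**The concern.** Blocked 1:1 allocation within clinic balances the arms inside each clinic. Differences between clinics in response level then largely cancel out of the home-office difference. An analysis that ignores clinic still counts that variation in its standard error, so the reported interval is wider than the design warrants. The reason that section 8.1 gives for adjusting for skin type applies equally to clinic, and the plan does not say why clinic is treated differently.

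What is at stake is efficiency. Each non-inferiority decision rests on one confidence bound. Section 8.3 sizes the trial on the skin-type analyses at 80% power with no stated allowance for loss, so those are the analyses where a slightly wide interval could matter.

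**Working it through.** **Inputs.** From section 8.3: 50% response in both arms, margin 15 percentage points (read as a lower bound above -15), one-sided 2.5%, 175 per arm per skin type. From section 3.1: about 80 patients expected in type V/VI, so the pooled total is 350 + 350 + 80 = 780, or 390 per arm. From section 4.3: 20 to 40 sites. Assumed, because the documents give no value: an ICC for clinic of 0.02 to 0.10 on the response scale. With p = 0.5, the SD of true clinic response rates is √(ICC × 0.25), which is 7, 11 and 16 points at ICC 0.02, 0.05 and 0.10.

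**Step 1: reproduce the plan's figures.** n = (1.960 + 0.842)² × 2 × 0.25 / 0.15² = 174.4, so 175 per arm. Power at 175 per arm is 80.1%. Pooled power is 99.8% at 525 per arm (the full 1050) and 98.7% at 390 per arm. The stated 175, 80% and 99% all reproduce, and they use the variance without clinic.

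**Step 2: effect of omitting clinic.**
- Reported SE = √(2 × 0.25 / n). At n = 175 this is 0.0535, a 95% half-width of 10.5 points.
- True SE under balance within clinic ≈ √(1 - ICC) × reported SE.
- Width ratio = 1 / √(1 - ICC).
- Power as planned = Φ[(0.15 - 1.96 × reported SE) / true SE].
- Power with clinic = Φ[0.15 / true SE - 1.96].
- Actual one-sided error as planned = Φ[-1.96 / √(1 - ICC)].

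Skin-type analysis, 175 per arm:

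| ICC (assumed) | Half-width with clinic (points) | Planned interval too wide by | Power as planned | Power with clinic | One-sided error as planned |
|---|---|---|---|---|---|
| 0 | 10.5 | 0% | 80.1% | 80.1% | 2.5% |
| 0.02 | 10.4 | 1.0% | 80.4% | 80.9% | 2.4% |
| 0.05 | 10.2 | 2.6% | 80.7% | 82.1% | 2.2% |
| 0.10 | 9.9 | 5.4% | 81.4% | 84.1% | 1.9% |

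Pooled analysis, 390 per arm, power as planned v with clinic: 98.8% v 98.9%, 98.9% v 99.0%, and 99.1% v 99.3% at ICC 0.02, 0.05 and 0.10.

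**Step 3: simulation check.** Sites of unequal size, blocks of two or four within site, raw risk difference against a Mantel-Haenszel risk difference stratified by clinic, 350 patients:

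| ICC | Sites | Mean SE, raw v stratified | Power, raw v stratified |
|---|---|---|---|
| 0 | 20 | 0.0533 v 0.0534 | 78.2% v 78.7% |
| 0 | 40 | 0.0533 v 0.0538 | 78.8% v 78.5% |
| 0.05 | 20 | 0.0532 v 0.0521 | 80.3% v 81.8% |
| 0.05 | 40 | 0.0533 v 0.0525 | 80.3% v 81.3% |
| 0.10 | 20 | 0.0531 v 0.0507 | 82.7% v 85.6% |
| 0.10 | 40 | 0.0532 v 0.0511 | 80.9% v 83.3% |

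With 780 patients and ICC 0.05 or 0.10, power differed by 0.1 points or less. With a true difference of -15 points, 30 sites and 4,000 trials, the raw analysis declared non-inferiority in 2.4%, 2.4% and 1.9% of trials at ICC 0, 0.05 and 0.10. The stratified analysis did so in 2.7% at each ICC. The Monte Carlo error is √(0.025 × 0.975 / 4000) = 0.25 points, so 2.7% is compatible with 2.5%.

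**The case against.** The strongest reply is that nothing promised is lost. The sample size was computed without clinic, so the planned analysis delivers its 80%. The pooled decision is effectively unaffected, and the error is on the safe side. The gain also depends on a between-clinic variance that nobody has stated. At a clinic SD of 0.3 on the logit scale (ICC about 0.02), a simulation with 350 patients and 40 sites gave 79.7% unadjusted v 79.3% stratified, with Monte Carlo error of about 0.8 points. With many small sites and modest clinic differences there may be no gain at all. All of this stands, and it limits the point to an efficiency improvement.

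The direction is also conditional. The interval is too wide if clinics differ in response level. If the home-office difference itself varies by clinic and the sites are viewed as a sample, both analyses are anti-conservative. With 350 patients, 30 sites, ICC 0.05 and an assumed effect SD of 5, 10 or 15 points, simulated one-sided error was 3.4%, 3.1% and 4.4% unadjusted, and 3.7%, 3.4% and 4.7% stratified (2,500 trials each). Adjusting for clinic does not cure this.

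The grounds for clinic differences have limits too. Sections 5.1 and 5.5 supply one home device type to all home patients, so devices can differ by site only in the office arm. The rater argument applies to the PGA and not to the patient-reported DLQI.

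What survives is that the plan adjusts for one stratification factor and omits the other without a reason, and that correcting this costs almost nothing.

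**Conclusion.** The mismatch between randomization and analysis is real, and its effect is small. For an assumed ICC of 0.02 to 0.10, the skin-type intervals are about 1% to 5% too wide, and about 0.5 to 3 points of power are forgone relative to a clinic-stratified analysis. The pooled analysis changes by at most 0.2 points at 390 per arm. These sizes rest on the assumed ICC, on 50% response, on 350 patients in each tested skin type, and on a home-office difference that does not vary by clinic.

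A reader might infer more, but the documents do not support it:
- **That the non-inferiority tests are invalid.** Under the stated assumptions, one-sided error falls to between 2.4% and 1.9%; it does not rise.
- **That the trial misses its planned power.** The 175 per arm already carries the variance without clinic, so 80% is met.
- **That the pooled conclusion is at risk.** Its power is about 99% either way.
- **That the safety comparison needs the same change.** Section 8.4.3 expects clinically significant burns in fewer than 1% of patients, and stratifying such rare events by clinic gains little.

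Low severity: a cheap improvement.

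**What to change.** - **Section 8.2.** Estimate each skin-type risk difference as a Mantel-Haenszel risk difference stratified by clinic. With 1:1 allocation the stratum weights, n₁n₀/(n₁ + n₀), are close to a quarter of stratum size, so the target stays practically the same as the raw difference.
- **Section 8.1.** Account for clinic as well as skin type in the pooled risk difference, using a method that tolerates small strata, for example Mantel-Haenszel. Clinic indicators in the logistic model are less suitable. Within a skin type there are only about 350/40 ≈ 9 to 350/20 ≈ 18 patients per clinic, and clinics where all or none respond would cause separation.
- **Both sections.** Fix a rule for pooling very small clinics before unblinding. It matters most for type V/VI, where about 80 patients over 20 to 40 sites gives 2 to 4 per clinic.

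The cost is SAP wording only, because clinic is already needed for randomization. There are two downsides. Clinics with patients in only one arm contribute nothing unless pooled. If clinics do not differ, a trivial amount of precision is lost: in the simulation at ICC 0 with 40 sites, the mean SE was 0.0538 against 0.0533, about 1%.

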8.3 Sample Size and Power Determination

Our study has been powered to allow us to determine non-inferiority of effectiveness both overall and within two of the three skin type strata. Because a clinical question is whether effectiveness is equivalent within each skin type sub-group, our sample size has been determined in order to provide adequate power for these skin type-specific analyses. We have pre-specified two primary effectiveness outcomes and assume a type I error rate for each outcome at the one-sided alpha = 2.5% level which is standard for a non-inferiority trial and analogous to the more familiar two-sided alpha = 0.05. Although this alpha level does not explicitly account for multiple comparisons, we believe that doing so would be unnecessarily conservative as both our patient-reported and physician-reported outcome measures assess the same outcome and are expected to be very highly correlated⁴⁶. Assuming a 50% response rate in both the office based phototherapy group and the home-based group and a non-inferiority margin of 15% (i.e. the 95% two-sided confidence interval on the difference in response rates between office and home-based groups excludes 15%), we calculated that 175 patients of each skin type would need to be included in each study arm to have 80% power to establish non-inferiority of home based phototherapy at a one-sided significance level of 2.5%. In the pooled sample, we will have 99% power for a non-inferiority

margin of 15%. Our non-inferiority margin has been iterated with our patient research partners and expert dermatologists. It is well within previous suggestions of non-inferiority for psoriasis treatments⁴⁷. We also note that the FDA accepts a 15% margin or greater for the study of biosimilars of biologics for moderate to severe psoriasis^{48, 49}. Additionally, our estimates are more conservative (i.e., require a larger sample size) than the non-inferiority margin specified in the pragmatic trial of home versus office based phototherapy conducted in the Netherlands which only required 100 patients per group total³⁰. Our estimates require a larger sample size compared to the Netherlands study primarily because we have set a higher bar for effectiveness. Based on preliminary data, the rate of DLQI ≤5 is anticipated to be similar to the estimate of achieving clear or almost clear skin, providing 80% power for the same non-inferiority margin for this outcome¹⁵.

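### The non-inferiority rule in section 8.1 sets the lower confidence bound against an unsigned 15% and gives no order of subtraction, so as written it is not a non-inferiority test

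*Combined protocol and SAP*

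**What the plan says.** Section 8.1 sets the hypothesis that "effectiveness of home-based UVB phototherapy will not be inferior to that of officebased phototherapy", for each of the two primary outcomes (PGA clear or almost clear; DLQI 0 to 5). It describes the effect measure thus: "Skin-type adjusted risk differences between home and office-based phototherapy will be computed from odds ratios using marginal standardization". The decision rule follows: home is non-inferior if the "lower bound of the adjusted two-sided 95% confidence interval for the risk difference is greater than the pre-specified non-inferiority margin of 15" percent.

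Section 8.2 carries the margin into the subgroup work: "separate analyses will be conducted for each skin type using a non-inferiority margin of 15" percent.

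Section 8.3 restates the criterion within the sample size argument, as the requirement that "the 95% two-sided confidence interval on the difference in response rates between office and home-based groups excludes 15" percent. There the arms are named in the opposite order to 8.1, and neither a bound nor a sign is given.

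The trial's margin appears five times (once in 8.1, once in 8.2, three times in 8.3), always unsigned. Nowhere is the difference defined as home minus office or as office minus home.

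**The concern.** An unsigned margin is ordinary shorthand for a size, and in most of these places it does no harm. In 8.1 it is the number that a lower confidence bound must exceed, and there the sign decides what is being tested.

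Both outcomes count responders, so a worse home arm gives a negative home-minus-office difference. A non-inferiority rule on that scale must allow a limited deficit. The rule in 8.1 allows none and demands a gain of more than 15 points. With the subtraction reversed, it rewards a proven deficit of more than 15 points. Neither version tests the hypothesis in 3.1 and 8.1.

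This sentence is the pass/fail threshold for the trial's main claim. A sound non-inferiority result would not meet the criterion as written, so the conclusion would have to depart from the plan's own text. Section 3.1.4 also has the analysts work with coded group labels, so the direction has to come from the written rule.

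**Working it through.** **Inputs.** Section 8.3: 50% response in both arms, margin 15 points, one-sided alpha 2.5% (z = 1.96), 80% power (z = 0.8416), 175 per arm per skin type, 99% pooled power. Section 3.1: 1:1 allocation. The pooled size is an assumption: 525 per arm from the 1050 randomized in 4.5, or 390 per arm from (350 + 350 + 80)/2, using the enrolment anticipated in 3.1. All figures use an unadjusted normal approximation.

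**1. Reproduce the plan's figures under the intended rule** (lower bound above −15 points, home minus office).

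- Required n per arm = (1.96 + 0.8416)² × 0.5 / 0.15² = 174.4, so 175. This matches the plan: "175 patients of each skin type would need to be included in each study arm to have 80% power".
- SE = √(0.5/n) = 0.0535 (n = 175), 0.0358 (390), 0.0309 (525).
- Power = Φ(0.15/SE − 1.96) = 80.1%, 98.7% and 99.8%. The plan states 80% per skin type and 99% pooled.
- If home is truly 15 points worse (35% against 50%), the pass probability is Φ(−1.96) = 2.5%, the stated alpha.

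An upper bound below +15 points on office minus home is the same test. In a simulation of 400,000 trials per size with Wald intervals, the two forms gave identical results: 0.793, 0.988 and 0.998 at the three sizes.

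**2. Apply 8.1 literally, home minus office** (lower bound above +15 points).

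- Pass probability with equal arms = 1 − Φ(0.15/SE + 1.96).
- Observed home lead needed at about 50% response = 0.15 + 1.96 × SE.

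| Per arm | Pass probability, 50% vs 50% | Plan states | Observed home lead needed | True home rate for an 80% chance, office 50% |
|---|---|---|---|---|
| 175 | 9.4e-7 | 80% | 25.5 points | 79% |
| 390 | 3.9e-10 | 99% | 22.0 points | 74% |
| 525 | 4.5e-12 | 99% | 21.0 points | 73% |

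**3. Apply 8.1 literally, office minus home** (lower bound above +15 points). Take home at 25% and office at 50%, a true deficit of 25 points.

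- SE = √((0.25 + 0.1875)/n).
- Pass probability = Φ((0.25 − 0.15)/SE − 1.96) = 85% (390 per arm) and 93% (525 per arm).

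**4. Check whether a minus sign alone repairs it.** It does not if the difference is taken as office minus home. With home truly 15 points worse (35% against 50%):

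- SE = √((0.25 + 0.2275)/175) = 0.0522.
- A lower bound above −15 points is met with probability Φ((0.15 + 0.15)/0.0522 − 1.96), which is more than 99.9% at 175 per arm and higher still at 525.

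Sign and order therefore both have to be stated.

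**The case against.** The strongest reply is that no competent reader would be misled. The sentence before the rule ties inference to non-inferiority principles, and the rule names a non-inferiority margin, meaning a largest acceptable deficit. The Study Summary lists office treatment as the reference therapy, and 8.1 mentions home first, so home minus office is the natural reading. The restatement in 8.3, taken as office minus home, already gives a workable criterion that agrees with the sample size. On this view the sentence needs a clarification, and the extreme probabilities describe an analysis that nobody would run. A minus sign could also have been lost when the PDF was read, since a hyphen is missing from a word in the same paragraph.

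Much of this stands. The intent is clear, and the probabilities do not forecast what an analyst would do. But clear intent does not make the stated threshold correct. Section 8.3 names neither the bound nor the sign, so it cannot override 8.1. A lost minus sign is possible but unlikely: the margin is unsigned in all five places, while negative study days in section 6.1 kept their signs. Even a restored sign would leave the order of subtraction undefined, and step 4 of the working shows that this matters.

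**Conclusion.** The concern holds and should be fixed. Under either order of subtraction, the rule in 8.1 is not the test that 8.3 powers. At the plan's own assumptions, the home-minus-office reading passes with probability 9e-7 per skin type and 4e-10 to 5e-12 pooled, where the plan states 80% and 99%. The office-minus-home reading would pass a home arm at 25% against 50% in 85% to 93% of pooled analyses.

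The sample size and stated power are sound for the intended rule. The pooled range rests on the assumed 390 to 525 per arm, and the planned skin-type adjustment would move the figures only slightly. Neither affects the conclusion.

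**What to change.** In 8.1, define the adjusted risk difference as the response proportion on home minus that on office. State that home is non-inferior on an outcome when the lower limit of the two-sided 95% CI for this difference lies above −15 percentage points. In 8.2, say that the skin-type analyses use the same sign and direction. In 8.3, replace the restated criterion with the same rule.

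The cost is wording in three sections. Sample size, alpha, stated power and the intended analysis do not change. Making the change before unblinding removes any suggestion that the rule was reinterpreted after the results were seen.
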